4.1. Inclusion Criteria

- 1) Age \geq 18 years.
- 2) The time from onset to randomization was within 12 hours.
- 3) Anterior circulation ischemic stroke was determined according to clinical symptoms and imaging examination.
- 4) Occlusion of the intracranial internal carotid artery, the M1- or M2-segment of the middle cerebral artery confirmed by CT angiography (CTA), MR angiography (MRA), or digital subtraction angiography (DSA).
- 5) Baseline National Institutes of Health Stroke Scale (NIHSS) ≥ 6.
- 6) Baseline Alberta Stroke Program Early CT Score (ASPECTS)<6.
- 7) Planned treatment with endovascular therapy (EVT).
- 8) Informed consent obtained from patients or their legal representative.

4.2. Exclusion Criteria

- 1) Intracranial hemorrhage confirmed by cranial computed tomography (CT) or magnetic resonance imaging (MRI).
- 2) mRS score \geq 2 before onset.
- 3) Pregnant or lactating women.
- 4) Allergic to contrast agents or glucocorticoids.
- 5) Participating in other clinical trials.
- 6) Systolic blood pressure >185 mmHg or diastolic pressure >110 mmHg, and oral antihypertensive drugs cannot control.
- Genetic or acquired bleeding constitution, lack of anticoagulant factors, or oral anticoagulants and INR > 1.7.
- 8) Blood sugar < 2.8 mmol/L (50 mg/dl) or > 22.2 mmol/L (400 mg/dl), platelet $< 90 \times 10^{9} \text{/L}$.
- 9) The artery is tortuous so that the thrombectomy device cannot reach the target vessel.
- 10) Bleeding history (gastrointestinal and urinary tract bleeding) in recent 1 month.
- 11) Chronic hemodialysis and severe renal insufficiency (glomerular filtration rate < 30 ml/min or serum creatinine > 220 umol/L [2.5 mg/ dL]).
- 12) Life expectancy due to any advanced disease < 6 months.
- 13) Follow-up is not expected to be completed.
- 14) Intracranial aneurysm and arteriovenous malformation.
- 15) Brain tumors with imaging mass effect.
- 16) Systemic infectious disease.

4.3. Criteria for Termination

Treatment of patients should be terminated if any of the following situations occur:

- 1) Voluntary withdrawal, which means withdrawal of informed consent. Patients are free to terminate or withdraw from the study at any time;
- 2) Objective disease progression of the patient (such as non-cerebrovascular diseases like tumors);
- 3) In the investigator's view, the patient intentionally or unintentionally fails to comply with the relevant provisions of the study, and it is necessary to terminate the treatment study.

Patients may withdraw from this trial at any stage for any reason. Similarly, the investigator has the right to terminate the enrollment of a patient in an emergency medical situation. For patients who withdraw from the study, the investigator must inquire about their reasons for withdrawal and whether any adverse events (AEs) have occurred. If the termination is caused by an adverse reaction, the AE must be followed up until it is properly resolved or the condition stabilizes. All existing study-related serious adverse events (SAEs) at the time of study termination must be followed up until they resolve, unless in the investigator's opinion, the condition is unlikely to resolve due to the patient's disease itself. The reasons and date of withdrawal from the study must be recorded on the case report form (CRF).

4.4. Privacy Protection

completely stored in the hospital where they receive treatment, and laboratory test reports and other examination results will be recorded in the patients' medical records. Only the investigators, ethics committees, and food and drug administration departments of this study will be allowed to access patients' medical records. Any public reports on the results of this study will not disclose the personal identities of patients. We will make every effort to protect the privacy of patients' personal medical information within the limits allowed by law.

According to medical research ethics, apart from personal privacy information, trial data will be available for public inquiry and sharing. Inquiry and sharing will be limited to web-based electronic databases to ensure that no personal privacy information is leaked.

5. Sample Size Calculation

Based on the research results from published literature and combined with clinicians' experience, the 90-day mortality rates for the intravenous methylprednisolone sodium succinate + endovascular treatment group (experimental group) and the placebo + endovascular treatment group (control group) are estimated to be 29% and 38%, respectively. Assuming a 1:1 ratio for the sample sizes of the two groups, a two-sided α of 0.05, and a power of 80%, the estimated sample size is 856 patients. Considering an expected dropout rate of 5%, the maximum estimated sample size, calculated using PASS 15.0, is 902 patients, with 451 patients in each of the intravenous methylprednisolone sodium succinate + endovascular treatment group (experimental group) and the placebo + endovascular treatment group (control group).

6. Randomization

6.1. Randomized Grouping

Patients are randomly divided into two groups in a 1:1 ratio. This trial employs block randomization for group assignment, generating a random sequence in a 1:1 ratio. Investigators at each sub-center report to the lead investigator after patients sign the informed consent form, and the latter implements randomized group assignment through a centralized network APP.

6.2. Concealing Group Allocation

- 1) This study employs a centralized randomization method. All odd and even random numbers in the random number sequence, generated by SAS software and corresponding to serial numbers (1, 2, 3...), are assigned to the experimental group and the control group, respectively, and recorded;
- A dedicated person is responsible for determining the grouping based on random numbers but does not participate in patient recruitment;
- The randomization schedule is sealed in opaque envelopes. The schedule is kept in triplicate, with one copy each retained by the principal investigator, the pharmacy, and the biostatistician. When unblinding or breaking the blind, the three copies of the randomization schedule must be opened simultaneously and in the presence of all parties. If one or more of the envelopes is damaged, it must be explained; otherwise, it will be announced that the grouping information has been leaked.

7. Blinding/Unblinding

This trial is blinded for investigators, patients, endpoint evaluators, and data analysts.

7.1. Implementation of Blinding

In this trial, a biostatistician generates two sets of random medication codes using a statistical software package.

The sponsor packages the medications according to the random codes, with the drug boxes labeled as "Medication for the MIRACLE Multicenter, Randomized, Double-Blind Clinical Trial of Early Combination Therapy with Methylprednisolone Sodium Succinate for Acute Large Core Infarct Recanalization." The label also indicates the drug code, random number, properties, specifications, production date, expiration date, storage conditions, and manufacturer.

The external packaging, color, and shape of the investigational drug and placebo are identical, making it impossible to distinguish between the experimental group drug and the control group drug. Grouping or treatment information is not known.

This trial uses envelopes to enclose emergency plans or/and the treatment regimens received by the subjects. This allows for unblinding in case of serious adverse reactions that require trial termination, ensuring prompt and appropriate treatment.

7.2. Emergency Unblinding Procedure

In case of emergency situations such as serious adverse events or when a patient requires urgent rescue, the responsible investigator at the center shall report to the sponsoring unit (The First Affiliated Hospital of Fujian Medical University) and the inspector to determine whether it is necessary to open the emergency envelope. Unblinding shall be performed based on the medication information provided in the emergency letter for the patient. The investigator shall complete the unblinding record form (Appendix II) and indicate it on the CRF. If the sponsor cannot be reached before unblinding, they shall be notified promptly after the unblinding. Once the emergency envelope is opened, the case shall be considered as a dropout and will not be included in the efficacy analysis. However, if there are adverse events, they shall be included in the adverse event analysis.

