The intention-to-treat analysis was chosen for statistical analysis of trial efficacy, and the per-protocol dataset (i.e., statistical analysis based on data from all patients who met the trial protocol criteria) was used as a reference. The \times 2 test or Fisher's exact probability method was used to compare event rates, while the t-test or Mann-Whitney U test was used to compare continuous variables. Superiority evaluation indicators were adopted, and statistical tests were performed at a two-sided significance level of 0.05. Differences with $P \leq 0.05$ were considered statistically significant. All statistical analyses were performed using SAS.

3. Programming and analysis of the statistical analysis system.

Trial Schedule	Serial Number	Phases	Start Date	End Date
	1	Preparation	2024-02-01	2024-07-31
	2	Execution	2024-08-01	2025-07-31
	3	Follow-up and Data Collection	2025-08-01	2025-10-31
	4	Data Processing and Analysis	2025-11-01	2025-11-30
	5	Summarizion	2025-12-01	2025-12-31

Table of contents

Lis	t of A	bbreviations	1
Stu	dy Sy	ynopsis	2
1.	Stud	dy Background	3
2.	Stud	dy Objectives	7
3.	Stud	dy Design	7
	Sele 4.1. 4.2. 4.3. 4.4.	tction of Patients, Criteria for Termination and Privacy Protection. 11 Inclusion Criteria 12 Exclusion Criteria 12 Criteria for Termination 12 Privacy Protection 12	1 2 2
5.	Sam	pple Size Calculation	3
	6.1. 6.2.	Randomization	3
	7.1. 7.2. 7.3.	Implementation of Blinding14Emergency Unblinding Procedure14Unblinding Regulations14	4 4
8.	Tre	atment	4
	8.1. 8.2. 8.3. 8.4. 8.5. 8.6.	Treatment Groups	5 5 5 6
9.	Scho	edule of Assessments	6
	9.1. 9.2. 9.3.	Collection of Baseline Data18Randomized Group18Follow-up18	8
10.	End	lpoints of the Clinical Trial	7
	10. 10.	Primary Endpoints	9 9
	10	.2.1. Secondary Efficacy Endpoints	9

The First Affiliated Hospital of Fujian Medical University

11. Adverse Events	. 20
11.1. Definition	. 20
11.1.1. Definition of Adverse Events (AE)	20

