10.1. Primary Endpoints

10.1.1. Primary Efficacy Endpoint

Mortality at 90±7 days.

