11.1.3. Definition of Serious Adverse Events (SAE)

SAE refers to events that occur during a clinical trial and result in: death; severe deterioration in the health of the patient, user, or others; life-threatening illness or injury; permanent impairment of body structure or bodily function; hospitalization or prolongation of existing hospitalization; medical or surgical intervention to prevent permanent impairment to body structure or bodily function, resulting in fetal distress, fetal death, or congenital anomalies/birth defects.

Note: Hospitalization that is planned in advance for pre-existing conditions or as required by the clinical trial protocol, without severe deterioration in health, is not considered an SAE.

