12.2. Statistical Analysis Sets

12.2.1. Full Analysis Set (FAS)

The Full Analysis Set (FAS) includes all patients who were enrolled, randomized, and received relevant interventions. Following the principle of Intent-to-Treat (ITT) analysis, patients who did not meet the inclusion criteria, did not receive relevant interventions after randomization, or had no evaluation results should be excluded from this dataset and not included in the statistical analysis. The FAS population is used for non-inferiority evaluation analysis of the primary evaluation indicators.

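### Emergency-unblinded patients leave the efficacy analysis although the trigger overlaps the mortality endpoint, and the full analysis set is not the ITT set that the plan promises

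*Combined protocol and SAP*

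**What the plan says.** The primary efficacy endpoint is "Mortality at 90±7 days" (10.1.1).

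Section 7.2 sets out when the emergency envelope may be opened: "In case of emergency situations such as serious adverse events or when a patient requires urgent rescue". The centre reports to the sponsoring unit and the inspector, and they decide whether opening is needed. The consequence for the analysis is: "Once the emergency envelope is opened, the case shall be considered as a dropout and will not be included in the efficacy analysis". The patient's adverse events still count in the adverse-event analysis.

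Section 11.1.3 begins its definition with "SAE refers to events that occur during a clinical trial and result in: death" and goes on to life-threatening illness and prolonged hospitalisation. Section 7.1 describes the purpose of the envelopes more narrowly: "This allows for unblinding in case of serious adverse reactions that require trial termination". Section 7.3 declares the double-blind trial invalid only if openings exceed 20%.

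On the analysis population, the synopsis says "The intention-to-treat analysis was chosen for statistical analysis of trial efficacy", and 12.3 repeats this with per-protocol as a reference. Section 12.2.1 says that the full analysis set (FAS) follows the ITT principle, but patients who did not meet the inclusion criteria, or who "did not receive relevant interventions after randomization, or had no evaluation results should be excluded from this dataset". It adds: "The FAS population is used for non-inferiority evaluation analysis of the primary evaluation indicators". The synopsis and 12.3 plan a superiority test at a two-sided 0.05.

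**The concern.** The patients most likely to be considered for emergency unblinding are those who are dying or at risk of dying. When they are removed from the efficacy analysis, the primary comparison is conditioned on a post-randomisation event that may lie on the path to the endpoint. A death could then be counted as an adverse event but not as a primary outcome. Unblinding does not make vital status at 90 days unobtainable, so valid primary data would be thrown away.

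Whether this biases the comparison depends on which patients are removed from each arm. Serious adverse events can depend on treatment (10.2.2 itself lists glucocorticoid-related events), so balance is not assured and the direction cannot be known in advance.

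The FAS problem is separate. A set that drops ineligible, untreated or unevaluated randomised patients is not ITT, whatever it is called. Its definition does not mention the exclusion in 7.2, and it is assigned to a non-inferiority analysis. The reader cannot tell which randomised patients enter the primary superiority test.

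**Working it through.** **Inputs.** From section 5: mortality 29% (active) and 38% (control), two-sided 0.05, power 80%, 1:1, 856 patients, 5% dropout, 902 in total (451 per arm). The documents do not give the number of openings, their split by arm, or mortality among the unblinded; these are assumptions.

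**The plan's own figure.** Unpooled normal formula: n = (1.960 + 0.842)² × (0.29×0.71 + 0.38×0.62) / 0.09² = 427.8, so 428 per arm and 856 in total. With dropout, 428/0.95 = 450.5, so 451 per arm and 902. The sample size reproduces and is not in dispute.

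**Method.** If a share f of the deaths in an arm with true mortality p is removed, observed mortality is p(1−f)/(1−pf) and the arm size is 451(1−pf). The probability of rejection comes from the two-sided pooled two-proportion z-test (normal approximation). With nobody removed and 29% against 38%, power is 81.8%.

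**Equal share of deaths removed, planned effect true.**

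| Share of deaths removed in each arm | Patients removed (total) | Power |
|---|---|---|
| 0% | 0 | 81.8% |
| 2% | 6 | 81.3% |
| 5% | 15 | 80.5% |
| 10% | 30 | 79.0% |
| 20% | 60 | 75.6% |
| 30% | 91 | 71.5% |

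At 10%, the observed rates are 26.9% and 35.6%, a difference of 8.7 points instead of 9.0. The risk difference shrinks but the odds ratio is unchanged. With no true effect, equal removal leaves type I error at 5.0%.

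**Unequal removal, no true effect (38% in both arms).** Worked case, 20% of active and 10% of control deaths:
- active: 0.38×0.80/(1−0.38×0.20) = 0.304/0.924 = 32.9%, with 451×0.924 = 417 patients left
- control: 0.38×0.90/(1−0.38×0.10) = 0.342/0.962 = 35.6%, with 451×0.962 = 434 left
- spurious difference 2.65 points; rejection probability 12.9%

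In the next table the number of openings is held fixed and mortality among the unblinded is varied.

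| Openings (active vs control) | All unblinded die | 80% die | 60% die | 38% die |
|---|---|---|---|---|
| 9 vs 4 (5% vs 2.5% of deaths) | 5.4% | 5.2% | 5.0% | 5.0% |
| 17 vs 9 (10% vs 5%) | 6.7% | 5.8% | 5.2% | 5.0% |
| 34 vs 17 (20% vs 10%) | 12.9% | 8.5% | 5.9% | 5.0% |

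Simulation with 400,000 trials per scenario gives the same values for the column in which all unblinded patients die.

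**Unequal removal, planned effect true.** Removing 5% of active and 10% of control deaths gives 28.0% against 35.6%, a difference of 7.6 points and power of 67.7%. Removing 10% of active and 5% of control deaths gives 26.9% against 36.8%, a difference of 9.9 points and rejection probability of 88.6%.

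**Fragility.** At exactly the planned rates (131/451 vs 171/451) p = 0.005. Removing 19 control deaths (152/432) gives p = 0.051.

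**Against the plan's own ceiling.** 20% of 902 is about 180 openings. The 12.9% case needs about 51, and 51/902 = 5.7%.

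**FAS exclusions unrelated to outcome.** Losing 5%, 10% or 15% of each arm gives power of about 79.8%, 77.6% or 75.3%.

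**The case against.** Five points deserve an answer.

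*Openings may be few and balanced.* Investigators, patients and evaluators are blinded, packaging is identical, and a serious adverse event does not open the envelope automatically. This stands as a reason not to predict bias. It does not justify the rule: case-by-case decisions on very sick patients give no protection against selection on outcome, and 7.1 and 7.2 describe different purposes for opening.

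*The larger error rates assume that every unblinded patient dies.* This stands. Urgent rescue and prolonged hospitalisation would bring in survivors. The second table shows the effect: 12.9% becomes 8.5% at 80% mortality, and there is no inflation once the unblinded die at the same rate as everyone else. The figures for the case in which all die are upper values for those numbers of openings.

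*The 20% limit in 7.3 is a safeguard.* Only in part. It lies far above the number of openings at which the comparison can already be distorted.

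*Some loss is already budgeted.* This stands. The 5% dropout allowance covers about 45 patients, and 79.8% power after a 5% neutral loss is essentially the 80% design target. Lost power is not the main issue.

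*A later statistical analysis plan will define the datasets (12.1.1), and the ITT intention is already stated.* The intention is clear, but 7.2 and 12.2.1 are current rules that contradict it. The FAS part is also the milder one: exclusion for baseline ineligibility need not depend on outcome.

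**Conclusion.** The concern holds. As written, 7.2 removes patients from a mortality analysis on a trigger that overlaps mortality, and nothing elsewhere in the plan restores them. If the same share of deaths is lost in both arms, type I error stays at 5% and the cost is some power, small at low rates. If the shares differ, the estimate can move in either direction: in the scenarios examined, type I error reaches between 5.4% and 12.9% when all unblinded patients die, and less when some survive. With the planned effect true, the observed difference ranges from 7.6 to 9.9 points. These figures rest on assumed opening rates; the documents give only the 20% ceiling.

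Independently of any rate, the FAS is not an ITT set, and its non-inferiority label leaves the population for the primary superiority test unclear.

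**What to change.** 1. In 7.2, delete the words that make an emergency-unblinded patient a dropout excluded from the efficacy analysis. State that the patient stays in the randomised arm and that 90-day vital status is obtained. The purposes of opening given in 7.1 and 7.2 should be reconciled; access to emergency unblinding need not change.
2. In 12.2.1, define the primary set as all randomised patients analysed as randomised, name it as the set for the primary superiority test, and reconcile the non-inferiority wording.
3. Seek 90-day vital status for every randomised patient, with a simple pre-specified sensitivity analysis for the few whose status is unknown.
4. Keep the FAS as 12.2.1 now defines it only as a sensitivity analysis, labelled modified ITT. If an analysis without unblinded patients is wanted, make that a sensitivity analysis too. Report openings by arm.

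The cost is wording in two sections and vital-status calls for unblinded or untreated patients. No extra patients are needed: with all 902 analysed, power at the planned rates is 81.8%.

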7.3. Unblinding Regulations

This trial employs a two-step unblinding method. After blinded verification and data locking, the staff responsible for keeping the blinded data at the statistical center performs the first unblinding, informing the biostatistician of the group corresponding to each case number using the codes A and B. This allows for statistical analysis of all the data. When the statistical analysis is complete and the final report is ready, a second unblinding is conducted at the clinical summary meeting to announce the exact groups represented by A and B.

If during the trial, the entire blinded data is leaked or the rate of emergency envelope opening exceeds 20%, this double-blind trial will be considered invalid.

8. Treatment

The emergency interventional team is on standby 24 hours a day, 7 days a week. Each sub-center screens patients according to the above inclusion and exclusion criteria, assigning them to the experimental group and the control group in a 1:1 ratio. After randomization, patients receive intravenous injections of methylprednisolone sodium succinate or placebo (i.e., methylprednisolone sodium succinate simulator) treatment as soon as possible. Relevant time points (accurate to the minute) are recorded faithfully and

accurately, and the efficacy and safety of the two treatment regimens are observed and evaluated.

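### Emergency code breaks remove patients from the efficacy analysis (7.2) and above 20% void the trial (7.3), although they can follow from the primary endpoint; both rules conflict with intention-to-treat in 12.3

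*Combined protocol and SAP*

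**What the plan says.** Section 7.2 covers emergency unblinding. It applies "In case of emergency situations such as serious adverse events or when a patient requires urgent rescue". The centre reports to the sponsoring unit and the inspector "to determine whether it is necessary to open the emergency envelope". Once an envelope has been opened, "the case shall be considered as a dropout and will not be included in the efficacy analysis"; adverse events in that patient still count in the adverse event analysis.

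Section 7.1 describes the purpose of the envelopes more narrowly: "This allows for unblinding in case of serious adverse reactions that require trial termination".

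Section 7.3 sets a limit for the whole trial. Apart from a leak of all the blinded data, if "the rate of emergency envelope opening exceeds 20%, this double-blind trial will be considered invalid". It gives no denominator for the 20%, no derivation, and no account of what being invalid means for the analysis.

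Section 11.1.3 puts death first among the outcomes that make an event serious: "SAE refers to events that occur during a clinical trial and result in: death". Section 10.1.1 gives the primary efficacy endpoint as "Mortality at 90±7 days". Section 12.3 says efficacy is analysed by intention to treat, with the per-protocol data as a reference. Section 12.2.1 lists who is left out of the full analysis set, and patients with an opened envelope are not on that list.

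**The concern.** Whether an envelope is opened is decided after randomisation, and the grounds for considering it overlap with the endpoint. A patient who is deteriorating or dying is more likely to be unblinded than one who recovers. Section 7.2 then takes that patient out of the comparison of deaths. The loss falls on events more than on survivors, so it lowers the observed mortality in both arms. If openings also differ by arm, for example because of steroid-related reactions, it biases the contrast itself.

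The exclusion gains nothing for the primary endpoint. Opening an envelope does not change the arm to which a patient was randomised, and recording a death needs no blinded judgement.

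Section 7.3 applies the same count to the trial as a whole. A high count may reflect high mortality or harm from the drug, and the rule responds by declaring the trial invalid without saying what happens to the randomised comparison. Below the limit the trial stands, even if the 7.2 exclusion has already removed many of its deaths.

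**Working it through.** **Inputs from the documents (section 5).** 90-day mortality 29% (experimental) and 38% (control), 1:1 allocation, two-sided α = 0.05, power 80%, 856 patients before dropout, 5% dropout, 902 in total (451 per arm).

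**Reproducing the plan's sample size.** With the unpooled normal approximation:

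n per arm = (1.960 + 0.842)² × (0.29×0.71 + 0.38×0.62) / 0.09² = 427.8, so 428 per arm and 856 in total.

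428 / 0.95 = 450.5, so 451 per arm and 902 in total. Both stated figures are confirmed.

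**How likely is the 7.3 limit to be crossed?** Take 902 as the denominator, which is an assumption because 7.3 gives none.

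- 0.20 × 902 = 180.4, so the rule applies from 181 openings.
- Average planned mortality is (0.29 + 0.38)/2 = 33.5%, so expected deaths are 0.335 × 902 ≈ 302.
- Share of deaths that would have to be unblinded if deaths were the only source: 0.20/0.335 = 59.7%. The range is 0.20/0.38 = 53% if mortality is 38% in both arms, to 0.20/0.29 = 69% if it is 29% in both.
- The opening rate is not in the documents. If 10%, 25%, 50% or 75% of deaths were unblinded, the rate from deaths alone would be 3.4%, 8.4%, 16.8% or 25.1%.
- The binomial chance of at least 181 openings in 902 is about 0 at a true rate of 10%, 0.00002 at 15%, 0.06 at 18%, 0.49 at 20% and 0.9998 at 25%.

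Openings for non-fatal serious events or urgent rescue would add to the count.

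**What does the 7.2 exclusion do below the limit?** Suppose a fraction f of deaths in each arm is opened and excluded, with no other loss. For an arm with true mortality p:

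- patients left: 451 × (1 − f·p)
- observed mortality: p(1 − f) / (1 − f·p)
- power ≈ Φ(d/SE − 1.96), where d is the difference in observed mortality and SE² = p₁(1−p₁)/n₁ + p₂(1−p₂)/n₂

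Example for f = 0.20:

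- Experimental: 451 × 0.942 = 424.8 patients, mortality 0.232/0.942 = 24.6%.
- Control: 451 × 0.924 = 416.7 patients, mortality 0.304/0.924 = 32.9%.
- d = 0.0827, SE = 0.0311, and power = Φ(2.66 − 1.96) = 76%.

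| Deaths opened, each arm | Patients excluded (of 902) | Observed mortality, experimental v control | Difference | Power |
|---|---|---|---|---|
| 0% | 0 | 29.0% v 38.0% | 9.0 points | 82% |
| 10% | 30 (3.4%) | 26.9% v 35.6% | 8.7 points | 79% |
| 20% | 60 (6.7%) | 24.6% v 32.9% | 8.3 points | 76% |
| 30% | 91 (10.1%) | 22.2% v 30.0% | 7.8 points | 72% |

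Exact binomial power of the chi-square test agrees to the nearest percent. If the planned 5% dropout occurs as well, power falls from about 80% to about 77% at f = 10% and about 73% at f = 20%. Every row lies well inside the 20% limit, so 7.3 would raise no objection to any of them.

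**The case against.** The strongest reply is that the rule counts openings, not deaths. Under 7.2 a serious event leads to a report and then a decision on necessity, and 7.1 describes a still narrower use. No section calls for opening an envelope because a patient has died. This stands. A reader might infer that, because planned mortality of 33.5% exceeds 20%, the endpoint alone could be expected to void the trial. The documents do not support that: it would need about 60% of deaths to be unblinded, and nothing in them points to such a rate.

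A reader might also set the 20% limit against the 5% dropout allowance in section 5 and call them inconsistent. They are different quantities: one is a ceiling on loss of blinding, the other an expected loss used for planning. Nor does the 7.3 clause itself reduce power. The loss comes from the 7.2 exclusion, so deleting only the 7.3 clause would restore none of it.

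It is also too strong to say that a harm signal would be thrown away. Section 7.3 does not say that data are discarded, 7.2 keeps adverse events in opened cases, and under 13.2 the DSMB receives a report after every 100 patients who complete follow-up and reviews all clinical and safety endpoint events.

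Finally, some concern about widespread unblinding is legitimate. Knowing the allocation can change later care, and decompressive craniectomy is itself a secondary endpoint, so even mortality could be affected. It would be wrong to say that code breaks can never matter. That supports monitoring and reporting them; it does not support excluding opened patients or invalidating the trial automatically on a count.

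**Conclusion.** The point holds, with its weight on 7.2. Excluding opened cases from efficacy contradicts 12.3, acts at any opening rate, and can remove patients because of the outcome being measured. If 10% to 30% of deaths in each arm were opened, power would fall from 82% to between 79% and 72%, and both mortality rates would be understated. Those fractions are assumptions, as are equal opening in the two arms and no other loss; the documents give no opening rate.

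The automatic invalidation in 7.3 is a poorly specified rule that is unlikely to be triggered: it has no denominator, no derivation and no stated consequence for the analysis. It is still worth replacing in advance, because invoking or waiving it once results are known would look data-driven. The sample size calculation is not in question.

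**What to change.** - **Section 7.2:** delete the sentence that makes an opened case a dropout excluded from efficacy. State that all randomised patients, opened or not, stay in the 90-day mortality analysis in the arm to which they were randomised.
- **Section 7.3:** replace automatic invalidation on the envelope rate with three items: the number, timing and reason of openings reported by arm; DSMB review of a high rate, with the denominator stated; and a sensitivity analysis for assessor-rated outcomes (mRS, EQ-5D VAS, symptomatic status of haemorrhage) that leaves out ratings made after a break. Keep the clause on a leak of the full list.
- **Sections 7.1 and 7.2:** reconcile the two descriptions of when an envelope may be opened. Which description applies is for the sponsor and investigators to settle.

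The cost is a few sentences in section 7 and one added sensitivity analysis. Treatment, visits and sample size do not change. The small downside is giving up a customary failed-blind rule. The change should be made before anyone sees unblinded results.
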